3.0 PATIENT ELIGIBILITY

3.1 Entry Criteria

Recurrent ultramutated/hypermutated endometrial cancer patients with measurable disease.

- 3.2.12 Patients are allowed to receive, but not required to receive, up to 4 additional lines of therapy.
- 3.2.13 At least 4 weeks must have elapsed since the patient underwent any major surgery (e.g., major: laparotomy, laparoscopy) There is no delay in treatment for minor procedures (e.g., tumor FNA or core biopsy, venous access device placement).

- 3.2.14 Have demonstrated adequate organ function as defined in Table 1. All screen labs should be performed within 14 days of treatment initiation
- Table 1
 Adequate Organ Function Laboratory Values

System	Laboratory Value		
Hematological			
Absolute neutrophil count (ANC)	≥1,500 /mcL		
Platelets	≥100,000 / mcL		
Hemoglobin	\geq 9 g/dL or \geq 5.6 mmol/L without transfusion or EPO dependency (within 7 days of assessment)		
Renal			
Serum creatinine OR	≤1.5 X upper limit of normal (ULN) OR		
Measured or calculated ^a creatinine			
clearance	\geq 60 mL/min for subject with creatinine levels > 1.5 X		
(GFR can also be used in place of	institutional ULN		
creatinine or CrCl)			
Hepatic			
Serum total bilirubin	≤ 1.5 X ULN OR		
	Direct bilirubin \leq ULN for subjects with total bilirubin levels $>$		
	1.5 ULN		
AST (SCOT) and ALT (SCDT)	≤2.5 X ULN OR		
AST (SOOT) and ALT (SOFT)	\leq 5 X ULN for subjects with liver metastases		
Albumin	$\geq 2.5 \text{ mg/dL}$		
Coagulation			
International Normalized Ratio (INR) or Prothrombin Time (PT)	\leq 1.5 X ULN unless subject is receiving anticoagulant therapy as long as PT or PTT is within therapeutic range of intended use of anticoagulants		
Activated Partial Thromboplastin Time (aPTT)	\leq 1.5 X ULN unless subject is receiving anticoagulant therapy as long as PT or PTT is within therapeutic range of intended use of anticoagulants		
^a Creatinine clearance should be calculated per institutional standard.			

- 3.2.15 Patients must have signed an approved informed consent and authorization permitting release of personal health information.
- 3.2.16 Patients must be 18 years or older

3.3 Ineligible Patients

- 3.3.1 Patients who have had prior therapy with nivolumab, pembrolizumab or with an anti-PD-1, anti-PD-L1, anti-PD-L2, anti-CTLA-4 antibody, or any other antibody or drug specifically targeting T-cell co-stimulation or immune check point pathways.
- 3.3.2 History of severe hypersensitivity reaction to any monoclonal antibody.
- 3.3.3 Patients with uncontrolled intercurrent illness including, but not limited to, ongoing or active infection, symptomatic congestive heart failure and unstable angina pectoris, cardiac arrhythmia, or psychiatric illness/social situations that would limit compliance with study requirements.
- 3.3.4 Patients who are pregnant or nursing. The effects of pembrolizumab on the developing human fetus are unknown. For this reason, women of child-bearing potential (WOCBP) must agree to use adequate

contraception (hormonal or barrier method of birth control; abstinence) prior to study entry and for the duration of study participation. WOCBP should use an adequate method to avoid pregnancy for 23 weeks after the last dose of investigational drug. WOCBP must have a negative serum or urine pregnancy test (minimum sensitivity 25 IV/L or equivalent units of HCG) within 24 hours prior to the start of pembrolizumab. Women must not be breastfeeding.

- 3.3.5 Women who are not of childbearing potential (i.e., who are postmenopausal or surgically sterile or have undergone definitive radiation) do not require contraception.
- 3.3.6 Patients with known brain metastases or leptomeningeal metastases are excluded unless the following conditions are met: Metastases have been treated and there is no evidence of progression by CT scan or magnetic resonance imaging (MRI) prior to the first dose of pembrolizumab administration). There must also be no requirement for immunosuppressive doses of systemic corticosteroids (>10 mg/day prednisone equivalents) for at least 1 week prior to study drug administration.
- 3.3.7 Patients should be excluded if they have known history of testing positive for human immunodeficiency virus (HIV) or known acquired immunodeficiency syndrome (AIDS). Patients should be excluded if they have a positive test for hepatitis B virus surface antigen (HBV sAg) or hepatitis C virus ribonucleic acid (HCV antibody) indicating acute or chronic infection (e.g., HCV RNA [qualitative] is detected).
- 3.3.8 Patients with active autoimmune disease or history of autoimmune disease that might recur, which may affect vital organ function or require immune suppressive treatment including systemic corticosteroids, should be excluded. These include but are not limited to patients with a history of immune related neurologic disease, multiple sclerosis, autoimmune (demyelinating) neuropathy, Guillain-Barre syndrome, myasthenia gravis; systemic autoimmune disease such as SLE, connective tissue diseases, scleroderma, inflammatory bowel disease (IRB), Crohn's, ulcerative colitis, hepatitis; and patients with a history of toxic epidermal necrolysis (TEN), Stevens-Johnson syndrome, or phospholipid syndrome should be excluded because of the risk of recurrence or exacerbation of disease. Patient with vitiligo, endocrine deficiencies including thyroiditis managed with replacement hormones including physiologic corticosteroids are eligible. Patients with rheumatoid arthritis and other arthropathies, Sjogren's syndrome and psoriasis controlled with topical medication and patients with positive serology, such as antinuclear antibodies (ANA), anti-thyroid antibodies should be evaluated for the presence of target organ involvement and potential need for systemic treatment but should otherwise be eligible.

NOTE: Patients are permitted to enroll if they have vitiligo, type I diabetes mellitus, residual hypothyroidism due to autoimmune condition only requiring hormone replacement, psoriasis not requiring systemic treatment, or conditions not expected to recur in the absence of an external trigger (precipitating event).

3.3.9 Patients should be excluded if they have a condition requiring systemic treatment with either corticosteroids (>10 mg daily prednisone equivalents) or other immunosuppressive medications within 14 days of study drug administration. Inhaled or topical steroids and adrenal replacement doses <10 mg daily prednisone equivalents are permitted in the absence of active autoimmune disease. Patients are permitted to use topical, ocular, intra-articular, intranasal, and inhalational corticosteroids (with minimal systemic absorption). Physiologic replacement doses of systemic corticosteroids are permitted, even if <10 mg/day prednisone equivalents. A brief course of corticosteroids for prophylaxis (e.g., contrast dye

allergy) or for treatment of non-autoimmune conditions (e.g., delayed-type hypersensitivity reaction caused by contact allergen) is permitted.

- 3.3.10 Patients who have had evidence of active or acute diverticulitis, intra-abdominal abscess, abdominal/pelvic fistula, gastrointestinal perforation, GI obstruction and/or who require parenteral hydration and/or nutrition..
- 3.3.11 Has a known history of active TB (Bacillus Tuberculosis)
- 3.3.12 Hypersensitivity to pembrolizumab or any of its excipients.
- 3.3.13 Prior invasive malignancy (except non-melanomatous skin cancer such as basal cell carcinoma of the skin or squamous cell carcinoma of the skin that has undergone potentially curative therapy or in situ cervical cancer) unless disease free for a minimum of 3 years.
- 3.3.14 Has a history of (non-infectious) pneumonitis that required steroids or current pneumonitis.
- 3.3.15 Has an active infection requiring intravenous systemic therapy.
- 3.3.16 Has a history or current evidence of any condition, therapy, or laboratory abnormality that might confound the results of the trial, interfere with the subject's participation for the full duration of the trial, or is not in the best interest of the subject to participate, in the opinion of the treating investigator.
- 3.3.17 Has known psychiatric or substance abuse disorders that would interfere with cooperation with the requirements of the trial.
- 3.3.18 Has not recovered from adverse events to <Grade 1 or prior treatment level due to a previously administered agent. Subjects with Grade <2 neuropathy or alopecia of any grade are an exception to this criterion and may qualify for the study.
- 3.3.19 Has a known additional malignancy that progressed or required active treatment within the last five years. Exceptions include basal cell carcinoma of the skin, squamous cell carcinoma of the skin that has undergone potentially curative therapy or in situ cervical cancer.
- 3.3.20 Is pregnant or breastfeeding, or expecting to conceive children within the projected duration of the trial, starting with the pre-screening or screening visit through 120 days after the last dose of trial treatment.
- 3.3.21 Patients should not have used investigational agents or device within 4 weeks prior to first dose.
- 3.3.22 Has received a live vaccine within 30 days of planned start of study therapy.

Note: Seasonal influenza vaccines for injection are generally inactivated flu vaccines and are allowed; however intranasal influenza vaccines (e.g., Flu-Mist®) are live attenuated vaccines, and are not allowed.

3.4 Inclusion of Women and Minorities

Women of all races and ethnic groups are eligible for this trial.

3.5 Identification of eligible patients

Archived tumor samples or newly obtained biopsies will be used for determining patient's eligibility. Identification of ultra-mutated (POLE/POLD1-mutation) and/or hyper-mutated (due to MMR gene defect) patients by standard PCR-based DNA microsatellite instability (MSI) and immunohistochemistry (IHC), and/or next generation sequencing (NGS) and Comprehensive Genomic Profiling (CGP) testing that is already standardized and performed in CLIA-certified laboratories at Foundation Medicine (18,19) without need for assay development.

4.0 STUDY MODALITIES AND TREATMENT MODIFICATIONS

4.1 The treatment to be used in this trial is outlined below in Table 2

Table 2Trial Treatment

Drug	Dose/Potency	Dose Frequency	Route of Administration	Regimen/Treatment Period	Use
Pembrolizumab	200 mg	Q3W	IV infusion	Day 1 of each 3 week cycle	Experimental

Please refer to the Investigator's Brochure for Preclinical and Clinical data on Pembrolizumab.

LABELING, PACKAGING, STORAGE AND RETURN OF CLINICAL SUPPLIES

Clinical Supplies will be provided by Merck as summarized in Table 3.

 Table 3 Product Descriptions

Product Name & Potency	Dosage Form
Pembrolizumab 50 mg	Lyophilized Powder for Injection
Pembrolizumab 100 mg/ 4mL	Solution for Injection

Packaging and Labeling Information

Clinical supplies will be affixed with a clinical label in accordance with regulatory requirements.

Clinical Supplies Disclosure

Drug identity (name, strength) is included in the label text; random code/disclosure envelopes or lists are not provided.

Storage and Handling Requirements

Clinical supplies must be stored in a secure, limited-access location under the storage conditions specified on the label.

Receipt and dispensing of trial medication must be recorded by an authorized person at the trial site.

Clinical supplies may not be used for any purpose other than that stated in the protocol.

Returns and Reconciliation

The investigator is responsible for keeping accurate records of the clinical supplies received from Merck or designee, the amount dispensed to and returned by the subjects and the amount remaining at the conclusion of the trial.

Upon completion or termination of the study, all unused and/or partially used investigational product will be destroyed at the site per institutional policy. It is the Investigator's responsibility to arrange for disposal of all empty containers, provided that procedures for proper disposal have been established according to applicable federal, state, local and institutional guidelines and procedures, and provided that appropriate records of disposal are kept.

4.2 Dose Selection/Modification

4.2.1 Dose Selection

Details on preparation and administration of pembrolizumab (MK-3475) are provided in the Pharmacy Manual.

4.2.2 Dose Modification (Escalation/Titration/Other)

Adverse events (both non-serious and serious) associated with pembrolizumab exposure may represent an immunologic etiology. These adverse events may occur shortly after the first dose or several months after the last dose of treatment. Pembrolizumab must be withheld for drug-related toxicities and severe or life-threatening AEs as per Table below.

irAE Toxicity	Hold Treatment For Grade	Timing for Restarting Treatment	Treatment Discontinuation		
Diarrhea/Colitis	2-3	Toxicity resolves to Grade 0-1	Toxicity does not resolve within 12 weeks of last dose or inability to reduce corticosteroid to 10 mg or less of prednisone or equivalent per day within 12 weeks		
	4	Permanently discontinue	Permanently discontinue		
AST, ALT, or	2	Toxicity resolves to Grade 0-1	Toxicity does not resolve within 12 weeks of last dose		
Bilirubin	3-4	Permanently discontinue (see exception below) ^a	Permanently discontinue		
Type 1 diabetes mellitus (if new onset) or Hyperglycemia	T1DM or 3-4	Hold pembrolizumab for new onset Type I diabetes mellitus or Grade 3-4 hyperglycemia associated with evidence of beta cell failure	Resume pembrolizumab when patients are clinically and metabolically stable		

Table 4 Dose Modification Guidelines for Drug-Related Adverse Events

	1	1	
irAE Toxicity	Hold Treatment For Grade	Timing for Restarting Treatment	Treatment Discontinuation
Hypophysitis	2-4	Toxicity resolves to Grade 0-1. Therapy with pembrolizumab can be continued while endocrine replacement therapy is instituted	Toxicity does not resolve within 12 weeks of last dose or inability to reduce corticosteroid to 10 mg or less of prednisone or equivalent per day within 12 weeks
Hyperthyroidism	3	Toxicity resolves to Grade 0-1	Toxicity does not resolve within 12 weeks of last dose or inability to reduce corticosteroid to 10 mg or less of prednisone or equivalent per day within 12 weeks
	4	Permanently discontinue	Permanently discontinue
Hypothyroidism		Therapy with pembrolizumab can be continued while thyroid replacement therapy is instituted	Therapy with pembrolizumab can be continued while thyroid replacement therapy is instituted
	2 ^b	Toxicity resolves to Grade 0-1	Permanently discontinue if toxicity develops despite adequate premedication ^d
Infusion Reaction	3-4	Permanently discontinue	Permanently discontinue
Pneumonitis	2	Toxicity resolves to Grade 0-1	Toxicity does not resolve within 12 weeks of last dose or inability to reduce corticosteroid to 10 mg or less of prednisone or equivalent per day within 12 weeks
	3-4	Permanently discontinue	Permanently discontinue
Nephritis (grading	Vephritis grading 2 Toxicity resolves to Grade 0-1 Toxicity does not corticosteroid to 1		Toxicity does not resolve within 12 weeks of last dose or inability to reduce corticosteroid to 10 mg or less of prednisone or equivalent per day within 12 weeks
according to increased creatinine or acute kidney injury)	3-4	Permanently discontinue	Permanently discontinue
Neurological	2 Toxicity resolves to Grade 0-1 Based on a		Based on severity of AE administer corticosteroids
Toxicities	3-4	Permanently discontinue	Permanently discontinue
1 Toxicity resolves to Grade 0		Toxicity resolves to Grade 0	Based on severity of AE administer corticosteroids
Myocarditis	2-4	Permanently discontinue	Permanently discontinue
Exfoliative DRESS			Based on severity of AE administer corticosteroids
Conditions	Confirmed SJS, TEN, or DRESS	Permanently discontinue	Permanently discontinue
All Other Drug- Related Toxicity ^c	Persistent Grade 2, 3 or Severe	Toxicity resolves to Grade 0-1	Toxicity does not resolve within 12 weeks of last dose or inability to reduce corticosteroid to 10 mg or less of prednisone or equivalent per day within 12 weeks
4		Permanently discontinue	Permanently discontinue

AE(s)=adverse event(s); ALT= alanine aminotransferase; AST=aspartate aminotransferase; DRESS=Drug Rash with Eosinophilia and Systemic Symptom; GI=gastrointestinal; ir=immune related; IV=intravenous; SJS=Stevens-Johnson Syndrome; T1DM=type 1 diabetes mellitus; TEN=Toxic Epidermal Necrolysis;

Note: Permanently discontinue for any severe or Grade 3 drug-related AE that recurs or any life-threatening event.

^b If symptoms resolve within one hour of stopping drug infusion, the infusion may be restarted at 50% of the original infusion rate (e.g., from 100 mL/hr to 50 mL/hr). Otherwise dosing will be held until symptoms resolve and the subject should be premedicated for the next scheduled dose; Refer to Infusion Treatment Guidelines for further management details.

^c Patients with intolerable or persistent Grade 2 drug-related AE may hold study medication at physician discretion. Permanently discontinue study drug for persistent Grade 2 adverse reactions for which treatment with study drug has been held, that do not recover to Grade 0-1 within 12 weeks of the last dose.

^d Patients with Grade 2 toxicity may continue therapy with pembrolizumab at the discretion of the Principal Investigator.

^a For patients with liver metastasis who begin treatment with Grade 2 AST or ALT, if AST or ALT increases by greater than or equal to 50% relative to baseline and lasts for at least 1 week then patients should be discontinued.

Dosing interruptions are permitted in the case of medical / surgical events or logistical reasons not related to study therapy (e.g., elective surgery, unrelated medical events, patient vacation, and/or holidays). Subjects should be placed back on study therapy within 3 weeks of the scheduled interruption, unless otherwise discussed with the Sponsor. The reason for interruption should be documented in the patient's study record.

In case toxicity does not resolve to Grade 0-1 within 12 weeks after the last infusion, trial treatment should be discontinued after consultation with Merck. With investigator, Merck and Sponsor agreement, subjects with a laboratory adverse reaction still at Grade 2 after 12 weeks may continue in the trial only if asymptomatic and controlled.

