- Renal Failure or Nephritis:
 - For Grade 2 events, treat with corticosteroids.
 - For Grade 3-4 events, treat with systemic corticosteroids.
 - When symptoms improve to Grade 1 or less, steroid taper should be started and continued over no less than 4 weeks.
- **Management of Infusion Reactions**: Signs and symptoms usually develop during or shortly after drug infusion and generally resolve completely within 24 hours of completion of infusion.

Premedication

at subsequent

		dosing
Grade 1	Increase monitoring of vital signs as medically	None
Mild reaction; infusion interruption	indicated until the subject is deemed medically	
not indicated; intervention not	stable in the opinion of the investigator.	
indicated		
Grade 2	Stop Infusion and monitor symptoms.	Subject may be premedicated 1.5h
Requires infusion interruption but	Additional appropriate medical therapy may	$(\pm 30 \text{ minutes})$ prior to infusion of
responds promptly to symptomatic	include but is not limited to:	pembrolizumab (MK-3475) with:
treatment (e.g., antihistamines,	IV fluids	
NSAIDS, narcotics, IV fluids);	Antihistamines	Diphenhydramine 50 mg po (or
prophylactic medications indicated for	NSAIDS	equivalent dose of antihistamine).
<=24 hrs	Acetaminophen	
	Narcotics	Acetaminophen 500-1000 mg po
	Increase monitoring of vital signs as medically	(or equivalent dose of antipyretic).
	indicated until the subject is deemed medically	
	stable in the opinion of the investigator.	
	If symptoms resolve within one hour of stopping	
	drug infusion, the infusion may be restarted at	
	50% of the original infusion rate (e.g., from 100	
	mL/hr to 50 mL/hr). Otherwise dosing will be	
	held until symptoms resolve and the subject	
	should be premedicated for the next scheduled	
	dose.	
	Subjects who develop Grade 2 toxicity despite	
	adequate premedication should be	
	permanently discontinued from further trial	
	treatment administration.	
Grades 3 or 4	Stop Infusion.	No subsequent dosing
	Additional appropriate medical therapy may	
Grade 3:	include but is not limited to:	
Prolonged (i.e., not rapidly responsive	IV fluids	
to symptomatic medication and/or	Antihistamines	

NSAIDS

Narcotics

Oxygen

Pressors Corticosteroids

Epinephrine

Acetaminophen

Table 5 Infusion Reaction Treatment Guidelines

Treatment

NCI CTCAE Grade

Appropriate resuscitation equipment should be available in the room and a physician readily available during the period of drug administration.

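### Grade 2 infusion reaction despite premedication: footnote d of Table 4 allows continuation, while the Table 4 cell it qualifies and Table 5 say to stop, and Table 5 does not carry the exception

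*Combined protocol and SAP*

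**What the plan says.** Three pieces of text bear on a patient who has a Grade 2 infusion reaction after adequate premedication.

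- **Table 4, Infusion Reaction, Grade 2, discontinuation column (section 4.2.2).** The cell reads "Permanently discontinue if toxicity develops despite adequate premedication" and carries footnote marker d.
- **Footnote d to Table 4.** "Patients with Grade 2 toxicity may continue therapy with pembrolizumab at the discretion of the Principal Investigator".
- **Table 5, Grade 2 row (section 4.6.1).** The condition is "Subjects who develop Grade 2 toxicity despite" adequate premedication. The action is that such patients should be "permanently discontinued from further trial" treatment. No exception or discretion is given.

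The two tables are linked. Footnote b, on the same Grade 2 row of Table 4, ends: "Refer to Infusion Treatment Guidelines for further management details".

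On who decides, section 10.1 describes one lead Principal Investigator covering Yale and all other sites. Section 10.9 uses the same title for the person responsible at each participating site.

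**The concern.** A stopping instruction for a safety event should give one answer. Here a clinician who reads Table 4 with its footnote finds that treatment may go on at someone's discretion. A clinician who reads Table 5, or who follows the pointer in footnote b to it, finds that treatment stops. Nothing says which table prevails.

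What is at stake is chiefly the individual patient, for whom the question is whether she is given the drug again. It is also a matter of oversight: with both instructions in force, a monitor cannot say whether continuing, or stopping, is a protocol deviation. Toxicity is a primary objective (section 1.1.2), so the rules that govern treatment after a toxicity ought to be unambiguous.

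**Working it through.** No arithmetic decides this point, and the plan states no figure to reproduce. The check is a comparison of the texts.

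**Step 1: is it the same event?** The Table 4 row is printed awkwardly in the text supplied, with the Grade 2 line appearing before its row label. Its content still identifies it. The cell speaks of premedication, and marker b on that line leads to a footnote about restarting the infusion at half rate, which Table 5 repeats in its Grade 2 row. The Table 4 cell and the Table 5 sentence therefore share one condition: Grade 2, despite adequate premedication.

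**Step 2: does footnote d reach that event?** In the text supplied, marker d appears on this cell and nowhere else in Table 4. By placement, it applies to this event. Its own words are broader: they mention Grade 2 toxicity but neither infusion reactions nor premedication. The link therefore rests on the marker.

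**Step 3: what does each text instruct?**

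| Text | Instruction | Discretion |
|---|---|---|
| Table 4 cell | Discontinue permanently | None in the cell itself |
| Footnote d to that cell | May continue | Principal Investigator |
| Table 5, Grade 2 row | Should be discontinued permanently | None |

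The cell and Table 5 agree. The departure is footnote d alone.

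**Step 4: does anything settle it?** Footnote b refers the reader from Table 4 to the infusion guidelines, and those do not mention footnote d. No sentence ranks one table above the other. Footnote d sets no criteria for continuing.

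**Step 5: who would decide?** Elsewhere the protocol separates the roles: section 9.2 distinguishes the Yale Principal Investigator from the sub-site investigator. Footnote d uses the bare title, which sections 10.1 and 10.9 apply to different people.

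**Step 6: how many patients?** The documents give no incidence. Purely as an assumption, take 1% to 5% of treated patients.

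- Maximum accrual of 25: 0.01 × 25 = 0.25 and 0.05 × 25 = 1.25.
- Minimum accrual of 8: 0.01 × 8 = 0.08 and 0.05 × 8 = 0.40.

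On that assumption, about 0 to 1 patient is expected.

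**The case against.** The best reply is that this is a rule with an exception. Qualifying a cell is what a footnote is for, so Table 4 is coherent taken alone. Table 5 says should rather than must, and it sits under guidance that section 4.6.1 introduces as suggested measures, so it could be read as supplementing Table 4. This much stands: the two tables are not flatly opposed, because Table 4's own cell agrees with Table 5. The defect is an exception that is not carried across. The reply does not remove it. Table 5 names no decision-maker and no condition for continuing, and it is the place to which footnote b sends the reader.

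A second reply is that the table was damaged in extraction and the marker may belong to another row. The marker and the sentences are legible where they stand, so this tempers certainty about the intended scope without removing the point. If the marker is misplaced, that also needs correcting.

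A third reply is that discretion held by one lead investigator would be exercised centrally, which would limit variation between sites. That holds only if the lead is meant, and the footnote does not say so.

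A reader might also infer that discontinuations and interruptions for toxicity will not be comparable across the trial. The documents do not support that. The trial has a single arm and makes no treatment comparisons (section 11, item a). Adverse events are summarised in a descriptive frequency table (section 11.2), and a reaction is recorded whether or not dosing continues. Section 7.1 provides for assessing treatment interruptions and says nothing of comparing discontinuations.

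**Conclusion.** The point holds as an internal inconsistency in a safety stopping rule, wrong as written. For one defined event, the Table 4 cell and Table 5 say to discontinue permanently, while footnote d allows continuation. The exception is missing from Table 5, and neither its scope nor its decision-maker is pinned down.

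Its statistical size is negligible. Sample size, alpha and power do not depend on it. Treated, eligible patients stay in the response analysis whether or not they stop (section 11.2), and the decision limits in Table 8 do not refer to discontinuation. The number of patients concerned is likely very small, though that rests on an assumed incidence. The reason to act is the clarity of a patient-safety instruction.

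The conclusion rests on the position of marker d as it appears in the text supplied. It implies no view on whether stopping or continuing is clinically right.

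**What to change.** Reconcile the Table 4 Grade 2 infusion reaction row, footnote d and the Table 5 Grade 2 row so that one instruction covers a Grade 2 reaction despite adequate premedication and reads the same in both places. If footnote d was meant for another row, move its marker. If discretion is kept, say which Principal Investigator holds it, the lead or the site's own, and carry the exception into Table 5. The choice of rule belongs to the sponsor and the clinical team.

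The cost is a wording amendment and its notification to sites. No design figure or analysis changes.
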